#### **Study Participants**

# Inclusion

Adults of 16 years or older who are treated as HAP within the two recruiting hospitals

#### **Exclusion**

- Intention is to palliate rather than cure
- Non-English speaking
- Patients from whom a sputum sample cannot be obtained within 6 hours of the administration of the first dose of antibiotics for this episode of HAP.\*

\*For the purposes of this protocol, if the patient has had prior instances of HAP during the same or a recent admission, a new episode of HAP is defined as occurring following a 48 hour cessation of prior antibiotics. In that circumstance a patient will be eligible for HAPOSS if a sputum sample can be obtained within 6 hours of the first dose of antibiotic for this new HAP episode.

In the circumstance where a patient is diagnosed with HAP whist receiving antibiotics for a non-respiratory infection e.g. cellulitis, if the HAP diagnosis leads to a change in the antibiotic prescription to cover the HAP then that patient will be eligible for recruitment to HAPOSS if the sputum sample was obtained within 6 hours of the first dose of the new/additional antibiotics for HAP. If the diagnosis of HAP does not result in a change in antibiotic then the patient is in-eligible.

# **Study Procedures**

Assessments	Day 1	Visit 1	Visit 2	Visit 3
Obtain sputum sample based on clinical indication (clinical team)	Х			
Process sputum through the FAPP (clinical team)	Х			
Discuss and provide information relating to the study (research team)		X*		
Obtain informed consent (research team)			Х	
Collection of clinical data from hospital record (research team)			Х	
Obtain consent# from patients that lacked capacity				X#

\*Visit 1 by the research team will occur as soon as they identify a patient's sample has been logged in the FAPP sample log — which will be reviewed each working day. During this visit, the study will be explained to the patient or consultee and a patient (or consultee) information leaflet will be provided. Visit 2 by the research team will be to obtain consent and this will occur after the patient has had time to consider the patient information leaflet and or discuss with family and or friends.

#A third visit will only occur in participants who lacked capacity at enrolment. This visit will be triggered by the indication from the clinical team that the participant may have regained capacity. The research team will stay in contact with the ward clinical team for the duration of the participants in patient stay in order to respond to the return of capacity.

#### Screening and eligibility

Participants will be identified from all wards in two the two participating hospitals. A series of education events will be run prior to and throughout the study period to raise awareness of the study. The decisions about whether to diagnose HAP, obtain a sputum sample for clinical diagnostics and to test a sub-sample of the sputum sample using the FAPP will rest with hospital clinical teams who will be made aware of the eligibility criteria. Eligibility criteria will be posted on all wards and above the FAPP machine. Prior to consent the research team will confirm eligibility.

#### Consent

The clinical team will obtain a single, clinically indicated sputum sample, as per usual care, and that sample will be immediately sub-sampled and run through the FAPP prior to being sent onwards, as usual, to microbiology. The data from the sample will be stored and the clinical team will have no access to this.

The patients' sample will be logged in the FAPP machine by means of a unique, 5-digit 'sample id'. Sample ids will consist of a site prefix followed by 3-digit consecutive sample numbers. For example, at Aintree all sample ids will have the prefix 01 and at the Royal Liverpool all sample ids will have the prefix 02 such that the first sample run at Aintree will be 01001 and the first at the Royal will be 02001 – the second Aintree sample will be 01002 and the second Royal sample will be 02002. The FAPP computer that holds this data will be password protected such that only members of the research team will be able to access this information. This FAPP log will be checked daily by the research team and new potential participants will be approached by the research team as soon as is practically possible. During this visit consent, or assent from a consultee will be obtained to analyse the stored sample data and for access to the standard medical record. In the situation where a patient declines consent or the consultee declines assent then the patient's data will not be included in the study.

Delivering interventions in an emergency setting makes HAP studies difficult and explains why there are so few. HAP has an inpatient mortality of over 25% and so it is important that research studies do not introduce undue delays to the clinical processes. Patients with HAP are more likely to be elderly and to have underlying cognitive impairment such as dementia. Moreover, HAP itself can cause transient delirium that impairs capacity. HAP occurs at any time of day and on any day of the week.

The above consent process represents a hybrid between a 'research without prior consent' model to process the sputum in the FAPP machine and a standard consent model with respect to the use and storage of data obtained from the analysis of the sputum. The 'research without prior consent model' is used frequently in intensive care and emergency scenarios where the delivery of the intervention is time critical. There are very limited risks associated with testing the sputum sample and so this model will place minimal burden on patients. Recent studies have revealed that patients and families are keen to embrace such consent models in order to conduct research aimed at improving outcome in HAP.[10]

# Patients without capacity to consent

HAP is more common in people with cognitive impairment. Moreover, HAP itself can induce delirium with consequent transient loss of capacity. Therefore, we must study patients who lack capacity in order for the findings of this study to be applicable to future research and to HAP in its usual clinical context.

The research has the potential to benefit future patients who have HAP and lack capacity. Our aim is to move from our current practice of empirical (best guess) antibiotic prescribing to a scenario where we prescribe the right antibiotic for the pathogen.

The benefits of this precision / personalised prescribing are that:

- a) getting the antibiotic right will improve efficacy of treatment
- b) avoiding broad spectrum antibiotics reduces the risk of antibiotic related adverse events such as C Diff diarrhoea
- c) reducing overall use of broad-spectrum antibiotics slows the development of antibiotic resistance

The research team will decide on a patient's capacity to consent to the study processes. All individuals specified with this role in the delegation log will be experienced in both clinical and clinical research settings and will be GCP trained.

If a patient is deemed to lack capacity to consent, we will contact a consultee in order to gain their assent to store the patient's information on our research data-base. The choice of consultee will default to the registered next of kin or person with legal power of attorney. Where neither of the above is available, a doctor, independent of the research team will be asked to consider the patients participation and act as a consultee. Ideally, this discussion will happen face-to-face and the consultee will sign an 'assent' form. When it is not possible to meet a consultee face-to-face we will speak to them on the phone and record their wishes on a date and timed 'assent form' along with the signature of the research team member involved. If no consultee is available then the patient's clinical consultant responsible for their care will be asked to consider their suitability for the study and to sign the assent form.

In the context of transient loss of capacity - at the point at which the patient regains capacity, they will be offered a patient information leaflet, the study will be explained by the study team and the patient will be asked to provide written informed consent. If the patient does not want to have their information stored as part of the study, all details will be removed from the study and their wishes will overrule any prior opinions of consultees.

# **Pseudo-anonymisation**

Patients will be assigned 4-digit study numbers using the following system:

Aintree Hospital recruits will have the prefix 1 followed by the consecutive 3-digit recruitment number – so the first recruit at Aintree will be 1001 and the second 1002 etc. The Royal Liverpool Hospital recruits will have the prefix 2 followed but consecutive 3-digit recruitment numbers – so that the first recruit at the Royal Liverpool will be 2001 and the second 2002 etc.

Participants will be identified only by their 4 digit study number in all but three circumstances: 1) the recruitment log where study numbers will link back to patient identifiers 2) the patient's consent form 3) the FAPP machine log where potential participants whose sputum has been run through the FAPP will be identified by name, hospital number and ward. At the end of the study the FAPP log will be permanently destroyed.

# Collection of hospital data

Once consent has been obtained, routinely available data recorded in hospital notes and on the hospital results system will be recorded in the case report form (CRF) by the research staff. This will include

demographics, the original reason for admission, routine medications and any antibiotics received since admission, lab results (full blood count, CRP, U+E at the time of HAP), known comorbidities.

# Definition of the end of study

The end of study is the date of agreement of the modified antibiotic guideline for the FAPP and it is anticipated this will be 12 months from the start of the study.

# Withdrawal of participants

Each participant has the right to withdraw consent from the study at any time. For those participants without capacity to consent to the study at the time of admission and who entered are the basis of assent gained from a consultee, withdrawal from the study may either be at the participant's own request (if they regain capacity) or at the request of a consultee. The participant and the consultee will be made aware that this will not affect the participant's future care. The reasons for leaving the study will be requested and recorded, but participants are not obliged to give reasons. Participants will be assured that withdrawal will not affect the future care they receive. All patient identifiers will be removed from the FAPP computer in the event of withdrawal from the study. All records of the patients FAPP sample will be removed from the study database and no clinical information relating to the patient will be stored.

# **Safety Reporting**

The definition of a serious adverse event (SAE) is problematic in the context of HAPOSS since participants will frequently be ill frail patients and mortality is high in this group.

All SAEs (defined below) will be recorded in the CRF but only those deemed to be SARs (defined below) will be reported.

The principal investigator at a site will need to distinguish between an SAE that is possibly, probably or definitely related to the intervention (= a suspected adverse reaction (SAR) – see definition below) and an SAE that arises from disease progression or has another cause.

# Serious adverse events (SAEs) Definitions

A serious adverse event is any untoward medical occurrence in a patient who receives a study intervention, which does not necessarily have to have a causal relationship with the intervention, in this case the testing of sputum by the FAPP, and that:

- Results in death,
- Is life-threatening (NOTE: The term "life-threatening" in the definition of "serious" refers to an event in which the participant was at risk of death at the time of the event; it does not refer to an event which hypothetically might have caused death if it were more severe.)
- Requires inpatient hospitalisation or prolongation of existing hospitalisation,
- Results in persistent or significant disability/incapacity, or
- Other important medical events (NOTE: Other events that may not result in death are not life threatening, or do not require hospitalisation, may be considered a serious adverse event when, based upon appropriate medical judgement, the event may jeopardise the patient and may require medical or surgical intervention to prevent one of the outcomes listed above.)

# **Serious Adverse Reaction (SAR)**

All untoward and unintended responses to a study intervention. The phrase "responses to the study intervention" means that a causal relationship between the study intervention and an AE is at least a reasonable possibility, i.e. the relationship cannot be ruled out. All cases judged by either the reporting medically qualified professional or the sponsor as having a reasonable suspected causal relationship to the trial intervention qualify as adverse reactions.

Since the results of the FAPP will not be available to the clinicians or the research team until after the last participants disease episode is over – the FAPP test itself will have no impact on patient care.

The only possible scenario we can foresee (and will mitigate against) is that, following testing on the FAPP the remaining sputum sample is lost and does not proceed to the microbiology lab – therefore depriving the patient of the potential of important diagnostic information. In the event that this occurred and the patient went on to suffer an SAE this could be interpreted as a SAR and would be reported.

# Reporting

Serious unexpected adverse reactions (SARs, defined above) are expected to be rare in this observational study but should be reported on an SAE form within 24 hours of being made aware of the event to the Sponsor. All other SAEs will be recorded in the CRF but not reported.

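### The 24-hour reporting rule adds an unexpectedness condition that the protocol's own definition of a SAR lacks, and the sponsor's causality role has no described route

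*Protocol*

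**What the plan says.** Three adjacent sections of the protocol govern safety reports.

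- **Safety Reporting.** "All SAEs (defined below) will be recorded in the CRF but only those deemed to be SARs (defined below) will be reported". The first sorting is done at site: "The principal investigator at a site will need to distinguish between an SAE that is possibly, probably or definitely related to the intervention". A related SAE is there equated with a SAR, expanded as a *suspected* adverse reaction.
- **Serious Adverse Reaction (SAR).** The heading expands the abbreviation as *serious*. The defining sentence covers any untoward and unintended response to the study intervention for which a causal link cannot be ruled out. Either of two parties can make that judgement: "All cases judged by either the reporting medically qualified professional or the sponsor as having a reasonable suspected causal relationship" to the intervention qualify. The section foresees a single harmful scenario, loss of the remaining sputum after the FAPP run. If the patient then has an SAE, "this could be interpreted as a SAR and would be reported".
- **Reporting.** This section carries the 24-hour clock: "Serious unexpected adverse reactions (SARs, defined above) are expected to be rare in this observational study but should be reported on an SAE form". It closes with "All other SAEs will be recorded in the CRF but not reported".

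**The concern.** Reporting is the section a site would follow when an event occurs. It contains a condition, unexpectedness, that appears in neither of the sections it relies on. The only harm the protocol names is one it has foreseen. A site that takes the adjective at face value could place that event among the other SAEs, which are recorded but not reported, although the preceding section says it would be reported.

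There is a second, separate gap. The definition gives the sponsor an independent say on causality. That say matters only when the site has judged an event unrelated, and those are the events that the reporting rule keeps in the CRF.

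At stake is whether both sites would handle the same event in the same way, and whether the causality assessment the protocol describes can be carried out. No estimate or analysis of the study depends on it.

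**Working it through.** No arithmetic applies: the protocol gives no figure here, and the point depends on no sample size or error rate. The check sets the three sections side by side.

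| Feature | Safety Reporting | Serious Adverse Reaction (SAR) | Reporting |
|---|---|---|---|
| Expansion of SAR | suspected | serious (heading) | serious unexpected |
| Seriousness required | yes, a SAR is a related SAE | not in the defining sentence | yes |
| Unexpectedness required | no | no | yes, as worded |
| Who judges causality | site principal investigator | reporting professional or sponsor | not stated |
| What is reported | all SARs | the specimen-loss case, explicitly | serious unexpected reactions only, as worded |

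Four test cases show where the sections part.

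1. **Specimen lost after the FAPP run, then an SAE judged related.** Safety Reporting: reported. SAR section: reported. Reporting, read literally: foreseen, so not unexpected, so recorded only. Reporting, read through its cross-reference to the definition above it: reported. The outcome depends on which reading the site adopts.
2. **Related SAE of a kind nobody foresaw.** Reported under all three sections. No conflict.
3. **Untoward but non-serious response to the intervention.** Within the defining sentence of the SAR section, but outside Safety Reporting, where a SAR is a kind of SAE, and outside Reporting, which requires seriousness.
4. **SAE that the site investigator calls unrelated but the sponsor would suspect.** Under the SAR section the sponsor's view is enough to make it a reaction. Under Safety Reporting, "only those deemed to be SARs (defined below) will be reported", and the site has not deemed it one. Under Reporting it stays in the CRF. No section says how the sponsor would learn of it.

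On case 4, Data handling and record keeping puts study data in a spreadsheet backed up to the University of Liverpool server, and Financing and Insurance names that university as sponsor. Even if SAE entries count as study data, the protocol does not say that the sponsor reviews them, and a backup is not a review. The items listed under Collection of hospital data include neither SAEs nor specimen loss.

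**The case against.** The strongest reply is that Reporting does not stand alone. Its parenthesis sends the reader back to the definition, which has no expectedness test. The SAR section says outright that the specimen-loss case would be reported, and Safety Reporting has all SARs reported. Two explicit statements and a cross-reference outweigh one adjective. This stands as far as it goes: a reader might infer that the rule bars reporting of the foreseen harm, and the documents do not support that. What remains is a conflict that the site must resolve for itself, in the section that sets the deadline.

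On seriousness, the heading of the SAR section, its worked example and Safety Reporting all imply it. That is fair, and the defect is limited to the sentence that does the defining.

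On the sponsor, the clause can be read as part of a definition rather than a promised procedure, and selective reporting is a reasoned choice. The protocol explains that participants are frail with high mortality and that FAPP results will not reach clinicians during care. The amendment history also records that the SAE wording was revised after external review. A reader might infer that the sponsor never receives the unreported events, or that all SAEs ought to be listed to the sponsor routinely. The first is too strong, because the spreadsheet is backed up on the sponsor institution's server. The second is a preference that the text does not compel, and a listing of SAEs with causality calls would not by itself reveal a lost specimen. The narrower point survives: a causality role is stated and no way of exercising it is described.

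**Conclusion.** The point holds as a minor correction to a safety instruction. The word *unexpected* in Reporting contradicts the two sections before it. SAR has three expansions and a defining sentence without a seriousness criterion. The sponsor's independent causality judgement has no described route for SAEs that the site calls unrelated. The conclusion rests only on the wording of the three sections and on the absence of any description of sponsor review elsewhere in the protocol.

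No magnitude should be attached. A reader might multiply the quoted inpatient mortality of over 25% by the target of 100 (100 × 0.25 = 25) and speak of 25 or more deaths kept from the sponsor. The protocol does not support that count: patients managed palliatively are excluded, inclusion depends on consent or assent obtained after the sample has been run, and there is no follow-up after consent. The number of deaths that would be recorded as SAEs cannot be derived. Nor do the documents show that the reporting rule defeats its safeguards as a whole: unforeseen related SAEs are reportable on every reading, and the foreseen one is reportable on the more natural reading.

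**What to change.** 1. In Reporting, delete *unexpected*.
2. In Safety Reporting, Serious Adverse Reaction (SAR) and Reporting, use one expansion and one definition: an SAE with at least a reasonable possibility of relation to the FAPP testing or to the handling of the specimen for it. State that it is reportable within 24 hours whether foreseen or not.
3. Reconcile the sponsor's role in one of two ways: describe a simple route by which the sponsor can assess SAEs that the site has called unrelated, or remove the sponsor from the causality clause so that the text matches the site-only assessment in Safety Reporting.

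Items 1 and 2 cost a wording change in a revised protocol version. Item 3 costs the same if the clause is removed, and some site and sponsor time if a review route is added. Expedited reporting can stay limited to SARs, for the reason the protocol already gives.

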#### Statistical considerations

This is an observational study and we will not be conducting and inferential analysis. We will describe the relative frequency of observation of bacterial, viral and antibiotic resistance gene detections. We will describe the relative frequency of demographics, cases per-ward, per-hospital etc. i.e. summary statistics.

# **Number of participants**

The sample size is pragmatic. Our recent audits of HAP cases demonstrate that Aintree hospital makes approximately 100 HAP diagnoses per-month with a slight seasonal bias towards an increase incidence in the winter. The Royal Liverpool has very similar rates. At both sites the rate of acquisition of sputum samples in routine clinical practice is 20%. Therefore, it there are 200 cases per month across both sites and sputum is acquired from 20% this means there will be 40 samples which could be tested per month. Assuming a 30% recruitment rate, this implies 12 samples per-month across the two sites. At this rate, our target of testing 100 samples will take approximately 8 months. This will enable us to recruit through a winter and into the summer to cover any seasonal variation in detections. Both hospitals are similar in terms of services, populations and protocols (and are now part of same trust) there is no scientific reason to insist on balanced recruitment. Recruitment will therefore continue until the target of 100 is reached.

#### **Ethics**

# **Declaration of Helsinki**

The Investigator will ensure that this study is conducted in full conformity with the current revision of the Declaration of Helsinki.

